**Background:**

The number of systematic reviews (SRs) indexed in PubMed continues to grow, highlighting the importance of well-written abstracts. Researchers often do not have the time or interest to read all of the available research and instead base their decision to read the full article on the information presented in the title and abstract. Abstracts should therefore reflect all the essential content of the main manuscript in an informative, accurate, attractive, and concise form that attracts researchers' attention.

Several articles have been published on how to write good abstracts, emphasizing that the abstract is one of the most important parts of the manuscript. Abstracts serve to 'sell' the work to editors, reviewers, and potential readers and help to improve the findability of the article. Due to the importance of the abstract, the preferred reporting items for systematic reviews and meta-analysis for abstracts (PRISMA-A) was developed in 2013 and updated in 2020^8. It provides guidance on which items should be reported in an abstract alongside with examples.

In our previous studies on the reporting of abstracts according to the PRISMA-A guidelines, we found that there are differences in structure, length, and reporting quality between Cochrane Reviews (CRs) and non-Cochrane Reviews (non-CRs). In particular, CRs are better reported and always structured. While non-Cochrane reviews consistently remain at a median length of 250 words, CR abstract's length has increased steadily from 353 words in 2000 to 838 words in 2022. It is questionable whether such long abstracts meet the goal of being informative, accurate, attractive, and concise. However, there are no guidelines regarding the optimal length of well-written SR abstracts, nor are there any studies indicating whether longer abstracts are more likely to attract readers' attention.

**Objective:****Primary:**

The primary aim of the study will be to investigate readers' attention of shorter versus longer abstracts, based on trial participation after reading the abstract.

**Secondary:**

The secondary objective will be to assess the perception of an abstract based on the four indicators of a well-written abstract, outlined by Bahadoran et al. These indicators state that abstracts should be: a) informative, b) accurate, c) attractive, and d) concise.

**Study design:**

This will be a two-arm, single-blinded, superiority, parallel-group randomized controlled trial (RCT) with 1:1 allocation of intervention and control groups.

**Reporting:**

This protocol was reported in line with the SPIRIT checklist.

**Study setting:**

The study will involve researchers from all over the world who recently published a SR, regardless of their research field.

**Participants:****Eligibility criteria**

The corresponding authors of SRs that were indexed in PubMed between January 1, 2024, and March 26, 2024, and for which an English abstract is available will be included. These include authors of all

types of SR as defined by Munn et al., with the majority likely representing SRs on effectiveness. Authors of other types of evidence syntheses (e.g. scoping reviews, methodological papers), editorials, protocols, corrections, retractions, errata, or summaries of SRs will be excluded. For identifying the SRs from which the corresponding authors will be contacted we will use the following eligibility criteria.

*Table 1 Eligibility criteria*

Inclusion	Exclusion
Systematic reviews of all types (Munn et al.  )	No English abstract
	Other types of evidence syntheses (e.g. scoping reviews, methodological papers)
	Protocols
	Editorials
	Others: e.g. Corrections, retractions, errata, or summaries of SRs
	No email address available

*Identification of participants:*

To identify eligible authors, MEDLINE (via PubMed) was searched with the following search strategy (date of search: 23.05.2024). To ensure the extracted contact data was up-to-date, we included SRs from January 2024 onwards until the minimum sample size of 6200 was reached. This was the case on March 26, 2024.

"systematic review"[Filter] AND ("2024/01/01"[Date - Entry]: "2024/03/26"[Date - Entry]) NOT ("1000"[Date - Publication]: "2023/12/31"[Date - Publication] OR "2024/03/27"[Date - Publication]: "3000"[Date - Publication])

All references will be screened by two reviewers independently. Articles that identify themselves as a study type other than SR, corrections or summaries in the title or abstract (e.g. explicitly labeled as a protocol or scoping review) will be excluded from this study. For all included SRs, the name, country, and email address of the corresponding author will be extracted manually from PubMed, the journal's page or the full text by the same independent reviewers. The extraction process will proceed according to the following procedure:

- If only one email address is provided in PubMed, this author is defined as the corresponding author.
- If multiple email addresses are provided, the first and then the last author will be given priority. If no e-mail address is provided for either of them, the first author to appear with an email address will be listed as the corresponding author.
- If there's no email address listed in PubMed, we will first search the journal page and then the full text to determine the identity of the corresponding author.
- If more than one email address is provided for a single author, the first email address and affiliation will be utilized.
- If no email address can be identified in PubMed the journal page or the full text, the article will be excluded.

All data is extracted from a single source, with PubMed being the primary source of information. If no information can be found in PubMed the journal page or the full text being consulted. The source of the information will be extracted. Disagreements between reviewers will be resolved by discussion or, if necessary, by a third reviewer.

Before randomization, duplicate e-mail addresses will be excluded using SAS for Windows version 9.4 (SAS Institute Inc, Cary, North Carolina) to prevent the cover letter from being sent to the same email address on more than one occasion.

***Intervention:***

In this study, we will attempt to emulate the reading process observed in PubMed. When searching PubMed, researchers are initially presented with an overview of the references identified. After clicking on the title, the corresponding abstract appears. For full-text access, researchers must actively follow a separate link to the journal page.

In this RCT, participants are randomly assigned to two groups (those receiving a long abstract vs. those receiving a short abstract). Both groups receive the same cover letter by e-mail explaining the purpose of the study, the use of the data, measures to ensure anonymity of participation and a link for participation. When participants click on the link, they automatically confirm their participation in the study.

The link will direct participants to SoSci Survey, an online survey tool. Those in the group receiving the long abstract will see an abstract with a length of 771 words (PMID: 37955353). Those in the group receiving the short abstract will see an abstract with a length of 277 words (PMID: 37942649). Both abstracts are structured and pertain to the same review by Soderberg et al. entitled "Percutaneous nephrolithotomy vs. retrograde intrarenal surgery for renal stones". This review was published once in the Cochrane Database of Systematic Reviews and once in the journal BJU International.

The design of the abstract presented is similar to that of PubMed, but no title or authors will be indicated. After reading the abstract, participants must actively click the "Continue" button to proceed.

***Outcomes:***

**Primary outcome:**

The primary outcome of this RCT will be the trial participation, which is defined as the proportion of participants who read the abstract and then clicked on the "Continue" button. This will be quantified by dividing the number of participants who read the abstract and proceeded to complete the survey by the total number of individuals who clicked on the link in the email. Information will be electronically captured in SoSci survey.

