**Secondary outcomes:**

The secondary outcomes will be the four criteria outlined by Bahadoran et al. as indicators of a well-written abstract:

- a) Informativeness
- b) Accuracy
- c) Attractiveness
- d) Conciseness.

The extent to which participants perceive these criteria to be fulfilled will be quantified on a 4-point Likert scale, e.g. very little informative, little informative, informative, very informative. For data analysis, the data will be dichotomized. For instance, the statements "very little informative" and "little informative" will be summarized in the category "non-informative," while the statements "informative" and "very informative" will be summarized in the category "informative."

Additionally, the time needed to read the abstract will be quantified. The time interval is defined as the period between the participant clicking on the link in the email and clicking on the „Continue" button to proceed to the survey. This time will be automatically recorded by SoSci Survey.

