**Sample size:**

Assuming an 80% trial participation in the control group, a two-sided significance level of 5% ( $\alpha = 0.05$ ), and a power of 90% ( $\beta=10\%$ ), 558 participants (279 per group) are needed to detect a relative difference in trial participation of 15% (80% vs. 68%). The sample size calculation was carried out using the PROC POWER function in SAS. Given an expected response of 9.6%, the sample size was estimated to be 5813. Additionally, expecting an approximately 5% exclusion due to study types other than SR^13 or duplicate email addresses, the sample size was increased to 6103. To achieve this, a total of at least 6200 SRs will be selected from PubMed and assessed for eligibility.

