**Recruitment and incentives**

The corresponding authors of the identified SRs will be contacted by email with a link to the survey and invited to participate. To achieve the highest possible response, recruitment will follow the recommendations for increasing the response of electronic questionnaires from Edwards et al..

Accordingly, we will:

- use a short and personalized cover letter that includes a picture
- use a simple but meaningful header, not including the term “survey”
- use a brief e-questionnaire that is designed in an attractive way
- give participants enough time, but also set and communicate a firm deadline.
- send the email by a female investigator.

The initial email invitation to participate in the study will be sent in August 2024. After two weeks, a first reminder will be sent out. A second reminder will be sent after four weeks. Data collection will conclude eight weeks after the initial e-mail has been sent.

No financial incentives are planned.

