***Statistical methods:***

Data will be analysed descriptively, using frequencies and proportions for categorical and means with standard deviations (SDs) as well as medians with interquartile ranges (IQRs) for continuous variables. All p-values less than 0.05 will be considered statistically significant. All statistical analyses will be conducted with SAS.

*Table 1. Variable, Measures, and Methods of Analysis*

Variable/Outcome	Outcome measure	Methods of analysis
Primary: Trial participation	Proportion (percentage) of participants who continued to participate after reading the abstract	Chi-square test
Secondary: Informativeness	Likert scale 1 to 4, dichotomized as informative and non-informative	Chi-square test
Secondary: Accuracy	Likert scale 1 to 4, dichotomized as accurate and non-accurate	Chi-square test
Secondary: Attractiveness	Likert scale 1 to 4, dichotomized as attractive and non-attractive	Chi-square test
Secondary: Conciseness	Likert scale 1 to 4, dichotomized as concise and non-concise	Chi-square test
Secondary: Time needed to read the abstract	Time spent on the first page that presents the abstract	Mann-Whitney U-Test

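### The only formula for the primary outcome counts survey completers, while the definition one sentence earlier counts people who clicked Continue

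*Combined protocol and SAP*

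**What the plan says.** The Primary outcome section contains two statements about the same quantity. The first defines trial participation as "the proportion of participants who read the abstract and then clicked on the" Continue button. The second gives the calculation as "dividing the number of participants who read the abstract and proceeded to complete the survey by the total number of individuals who clicked", meaning those who followed the e-mail link.

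Two other sections show where the click falls. The Intervention section says "After reading the abstract, participants must actively click the" Continue button in order to move on. The Secondary outcomes section, defining reading time, ends the interval at the click on the Continue "button to proceed to the survey. This time will be automatically recorded by SoSci Survey". So the click comes after the abstract page and before the questions.

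Elsewhere the outcome is only named or paraphrased. The primary objective is "based on trial participation after reading the abstract". The analysis table under Statistical methods has "Proportion (percentage) of participants who continued to participate after reading the abstract", tested by chi-square. The Sample size section applies 80% and 68% to trial participation without naming the event.

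**The concern.** Clicking Continue and completing the survey are different events, separated by the whole questionnaire: four ratings of the abstract, plus items on abstract features and participant characteristics. The two sentences classify anyone who starts the questionnaire and does not finish it in opposite ways.

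The objective is attention to the abstract. A completion numerator adds drop-off during the questionnaire, which arises after the abstract page and may have other causes. The formula is also the sentence a programmer would code, because it alone sets out a numerator and a denominator explicitly. While both sentences stand, either numerator could be defended after the data are seen, and no section says how partial completers are counted.

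**Working it through.** **Inputs.** From Sample size: 80% vs 68%, two-sided alpha 0.05, 90% power, 279 per group. From Statistical methods: chi-square test. Abandonment after Continue, *a*, is not in the documents; 2%, 5%, 10% and 20% are assumed, equal in both arms. The 80% and 68% are taken as Continue rates, and the 279 per arm as link-clickers, the formula's denominator.

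**Step 1: reproduce the plan's figure.** With pooled variance and no continuity correction,

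n = [1.960·√(2·p̄(1−p̄)) + 1.2816·√(p₁(1−p₁)+p₂(1−p₂))]² / (p₁−p₂)²

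Here p̄ = 0.74, so n = (1.2158 + 0.7875)² / 0.12² = 278.7, rounded up to 279 per group and 558 in total. This matches the plan. It does not show which numerator was meant.

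**Step 2: power if completion is analysed.** The rates become 0.80(1−a) and 0.68(1−a). The ratio stays at 0.85 while the difference shrinks. Power is Φ{[d·√279 − 1.960·√(2·p̄(1−p̄))] / √(p₁(1−p₁)+p₂(1−p₂))}, where d = p₁−p₂.

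| Assumed abandonment | Completion rates | Difference (points) | Power |
|---|---|---|---|
| 0% | 80.0% vs 68.0% | 12.0 | 90.0% |
| 2% | 78.4% vs 66.6% | 11.8 | 87.7% |
| 5% | 76.0% vs 64.6% | 11.4 | 84.0% |
| 10% | 72.0% vs 61.2% | 10.8 | 77.3% |
| 20% | 64.0% vs 54.4% | 9.6 | 63.6% |

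**Step 3: the test result at the planned difference.** Counts are out of 279 per arm, with abandoners rounded to whole persons and no continuity correction.

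| Numerator | Counts | Chi-square | p |
|---|---|---|---|
| Continue | 223 vs 190 | 10.15 | 0.0014 |
| Completion, 2% abandon | 219 vs 186 | 9.81 | 0.0017 |
| Completion, 5% | 212 vs 180 | 8.78 | 0.0030 |
| Completion, 10% | 201 vs 171 | 7.26 | 0.0071 |
| Completion, 20% | 178 vs 152 | 5.01 | 0.025 |

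All are significant, so at this observed difference the conclusion does not depend on the numerator.

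**Step 4: where the two numerators disagree.** Fix one arm at 223 of 279 Continue clicks and raise the other arm's count from 190. The Continue test stays significant up to 203 (p = 0.046; 204 gives 0.058).

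| Assumed abandonment | Other-arm Continue counts significant on Continue but not on completion | Completion p at the lowest such count |
|---|---|---|
| 2% | 203 | 0.051 |
| 5% | 202–203 | 0.058 |
| 10% | 200–203 | 0.056 |
| 20% | 195–203 | 0.057 |

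In Continue terms these are observed differences from (223−203)/279 = 7.2 points to (223−195)/279 = 10.0 points.

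**Step 5: unequal abandonment, illustration only.** Suppose Continue is 80% in both arms and completion among those who continue is 90% vs 80%. The literal formula then compares 0.80 × 0.90 = 72% with 0.80 × 0.80 = 64%. At 279 per arm the test is significant about 53% of the time although the Continue outcome does not differ. Nothing in the documents says whether such a gap is likely.

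**The case against.** The best defence is that there is one endpoint, loosely described. The second sentence sets out to quantify what the first has just defined, and its phrase about completing the survey can mean simply going on to fill it in. The Intervention and Consent sections treat the link click as confirming participation, so the definition already implies Continue clicks over link clicks. The objective and the analysis table fit that reading, and no other section makes survey completion an outcome. On size, every abandonment rate above is assumed, and the protocol intends to "use a brief e-questionnaire that is designed in an attractive way", so the true rate may be small. At 2% the loss is about two points of power and a single discordant count. The power loss also requires 80% and 68% to be Continue rates, which the Sample size section does not state. Had they been planned as completion rates, analysing completion would lose nothing.

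Most of this stands as a reading of intent: the text leans towards the click. It does not remove the problem, because the formula coded as written returns completion and no section says how abandoners count. Taking the planning rates as Continue rates is reasonable, since that section uses the term defined by the click, but it is an inference.

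**Conclusion.** The concern holds. The definition and the formula for the sole primary outcome name different events, and the plan does not say which governs. This is an inconsistency in the endpoint, not an error in the sample-size arithmetic.

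Its practical size cannot be fixed from the documents. It is nil if everyone who clicks Continue finishes, modest at a few per cent abandonment, and material at 10% to 20%, always supposing equal abandonment and Continue-based planning rates. Step 3 describes observed counts; even with a true 80% vs 68%, sampling variation can produce a smaller observed difference at which the two numerators disagree. It should be fixed because it concerns the only primary outcome and leaves the choice of numerator open after the data are seen.

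**What to change.** - **Primary outcome:** replace the completion wording in the formula with the Continue click, keeping everyone who clicked the e-mail link as the denominator. People who click Continue and then abandon the survey are thereby counted as successes.
- **Statistical methods, analysis table:** name the Continue click as the event.
- **Sample size:** state that 80% and 68% are Continue rates, with the authors confirming that this is what they planned.
- **Optional:** report survey completion by arm as a separate descriptive outcome, which would show any differential drop-off.

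The cost is a few words in three sections. The survey tool is already set to record the time to the Continue click, so no new data are needed. The chi-square test is unchanged, and with the planning rates stated as Continue rates the 558 stands.

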**Allocation:**

**Sequence generation and implementation:**

In a 1:1 ratio, the corresponding authors will be randomly assigned to either the group receiving the long abstract or the group receiving the short abstract using the PROC PLAN procedure in SAS.

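### Does the primary outcome need a stated rule for authors who open the survey link more than once?

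*Combined protocol and SAP*

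**What the plan says.** The primary outcome is trial participation. The numerator is those who read the abstract and go on through the survey, divided "by the total number of individuals who clicked on the link in the email". The table under Statistical methods describes the same measure as "Proportion (percentage) of participants who continued to participate after reading the abstract" and assigns it a chi-square test.

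The unit of randomisation matches: "the corresponding authors will be randomly assigned to either the group receiving the long abstract or the group receiving the short abstract" (Sequence generation and implementation). Under Participants, the list of addresses is cleaned first: "Before randomization, duplicate e-mail addresses will be excluded using SAS for Windows version 9.4".

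Under Recruitment and incentives, the invitation goes out in August 2024. Then: "After two weeks, a first reminder will be sent out. A second reminder will be sent after four weeks". Collection closes at eight weeks. The same section promises to "use a short and personalized cover letter that includes a picture". The Intervention section says that the letter covers "measures to ensure anonymity of participation and a link for participation". Ethical approval states that data are collected anonymously, and Confidentiality states that no personal data are collected.

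Reading time is defined twice. Secondary outcomes runs it from the click on the e-mailed link to the Continue button. The Statistical methods table takes it as time on the page that shows the abstract.

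**The concern.** A person can be counted once only if the survey record shows that two openings came from the same person. The plan describes no per-recipient link, no limit of one response and no rule for repeat openings. The only de-duplication acts on e-mail addresses before randomisation, which does not touch repeat visits. Three e-mails over eight weeks invite one kind of repeat in particular: someone opens the link, leaves at the abstract and comes back after a reminder.

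If the link carried only the arm, such visits could not be merged later and the denominator would drift from people to openings. Opening the link displays the randomised abstract, so re-opening happens after exposure and could differ between the 771-word and 277-word arms. That would put a spurious component into the only primary comparison, and it could not be repaired after data collection. Reading time would raise a related question, because such a person has two clicks.

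**Working it through.** **1. The plan's own figure.** Inputs from Sample size: 80% vs 68%, two-sided alpha 0.05, power 90%. With the pooled-variance formula and mean rate 0.74:

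n = [1.960·√(2·0.74·0.26) + 1.282·√(0.80·0.20 + 0.68·0.32)]² / 0.12² = (1.216 + 0.788)² / 0.0144 ≈ 279 per arm, 558 in total.

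This reproduces the plan. With one record per person, power is 0.90.

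**2. Unfinished repeats counted as failures.** Let p be the person-level rate, and let rc and rn be the shares of continuers and non-continuers who make one extra opening that stops at the abstract. The expected observed rate is p / (1 + p·rc + (1 − p)·rn). All values of rc and rn are assumptions. Power and type I error come from 400,000 simulated trials with 279 people per arm and an uncorrected chi-square test; type I error is at 80% in both arms.

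| Assumed re-opening, equal in both arms | Observed rates | Power | Type I error |
|---|---|---|---|
| none | 80.0% vs 68.0% | 0.902 | 0.051 |
| 2% of everyone | 78.4% vs 66.7% | 0.886 | 0.050 |
| 5% of everyone | 76.2% vs 64.8% | 0.863 | 0.048 |
| 10% of everyone | 72.7% vs 61.8% | 0.829 | 0.045 |
| 10% of continuers | 74.1% vs 63.7% | 0.806 | 0.034 |
| 20% of non-continuers | 76.9% vs 63.9% | 0.914 | 0.080 |

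For example, 10% of continuers gives 0.80/1.08 = 74.1% and 0.68/1.068 = 63.7%.

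**3. Rates that differ by arm.** With true rates of 80% vs 68%, let 10% of continuers reopen in the 80% arm and 5% in the other. The observed rates are 0.80/1.08 = 74.1% and 0.68/1.034 = 65.8%, a difference of 8.3 points, and power is about 0.60. With the two re-opening rates swapped, the observed rates are 76.9% and 63.7%, and power is about 0.95.

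With 80% in both arms, 5% vs 10% of continuers gives 76.9% vs 74.1% and a type I error of about 0.11. For 10% vs 20% the figures are 74.1% vs 69.0% and about 0.27.

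**4. Whether that last difference is false.** For people who leave and later continue, it is false only if any opening before the close decides the outcome. If the first opening decides, they are failures. When all the extra openings are of that kind, 10% vs 20% of continuers gives first-opening rates of 0.80·0.90 = 72% and 0.80·0.80 = 64%. That is a real 8-point difference, larger than the 5.1 points observed. Leaving the longer text on the first visit is arguably part of the attention effect under study.

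**5. The case that reminders invite.** Let a be the chance of continuing at the first opening (0.80 and 0.68), g the share of leavers who return once, and h their chance of continuing then, with g and h equal by arm. The person-level rate by any opening is a + (1 − a)·g·h. The rate by openings is that figure divided by 1 + (1 − a)·g.

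| g, h | Difference, first opening | Difference, all openings counted | Difference, any opening |
|---|---|---|---|
| 0.10, 0.5 | 12.0 | 12.0 | 11.4 |
| 0.25, 0.5 | 12.0 | 11.9 | 10.5 |
| 0.25, 1.0 | 12.0 | 10.6 | 9.0 |
| 0.50, 0.5 | 12.0 | 11.8 | 9.0 |

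Differences are in percentage points. Here even a count of openings falls between the two reasonable person-level answers, to rounding.

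**6. Reading time.** The interval ends at Continue, so an abandoned visit yields no time of its own. The page-based measure in the Statistical methods table makes the visit that ended in Continue the natural one to use. A problem arises only if a first click is paired with a later Continue.

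**The case for a change.** The strongest case for a change is about timing. If links carry only the arm, nothing done after the close can restore the person-level denominator, whereas one random serial per address before launch would secure it. The letter is already personalised, so the technical effort is small. The outcome at risk is the only primary one, and step 3 shows that arm-dependent re-opening at 10% vs 20% would seriously distort the test.

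Part of this stands. The gap in the text is real, the formulas hold, and no one can say from the documents how often authors would reopen the link.

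The rest is conditional. The documents do not say that links are arm-level only. The cover letter and the figure under Participant timeline, either of which might cover link handling or reminders, were not available. The larger effects need sizeable or clearly unequal re-opening. A completed repeat would add a success, which the simulations leave out. If the long abstract is both the lower-participation arm and the more often reopened one, the distortion raises power to about 0.95 but also enlarges the apparent effect.

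Nor is the remedy free. A list linking serials to addresses would make responses, including age, gender and country, traceable during collection. The statements under Ethical approval, Consent and Confidentiality would need revisiting, and so would the basis of the ethics waiver. Whether that exchange is worthwhile is open to debate.

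**Conclusion.** No change to the plan is called for. The outcome definition and the unit of randomisation agree: both are the person. Followed as written, the analysis counts each individual once, and 279 per arm gives 90% power. What is missing is how the survey tool delivers that count, an operational detail that a competent team can be expected to settle when it builds the links and cleans the data.

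The consequence of counting openings instead cannot be sized from the documents. On assumed equal rates of 2% to 10% of everyone, it costs about 2 to 7 points of power and leaves type I error at or below 5%. Equal re-opening confined to non-continuers raises type I error, to about 8% at an assumed 20%. Larger harm needs arm-level links together with re-opening that differs materially between arms, and the documents establish neither. Evidence of both would reopen the question. As things stand, a strict remedy would give up some of the stated anonymity to guard against an unproven problem.
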